## 2 Study Objective and Clinical Hypotheses

## 2.1 Study Objective

To evaluate the safety and tolerability of treatment with atogepant 60 mg QD when administered over 52 weeks for the prevention of migraine in participants with EM.

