The study will consist of a 4-week screening and baseline period, a 52-week treatment period, and a safety follow-up period of 4 weeks. *De Novo* Participants and Study CGP-MD-01 Completers will complete all 16 study visits, including the 28-day screening period.

For clarity, note that the participant must not be randomized until Visit 2 when eligibility has been confirmed.

After the randomization visit, the study visits will occur every 4 weeks for the duration of the 52-week treatment period. Participants will return to the clinic for safety assessments at 4, 8, 12, 16, 20, 24, 28, 32, 36, 40, 44, 48, and 52 weeks relative to their randomization visit. A safety follow-up visit will occur 4 weeks after the last dose of atogepant 60 mg QD or after the last study visit for the SOC arm. For details, please see Table 1, Schedule of Visits and Procedures.

The primary objective of the study is to assess the safety and tolerability of long-term atogepant treatment. The planned safety assessments include collection of AEs, clinical

laboratory determinations, ECGs, vital sign measurements, physical examinations, and the C-SSRS.

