## 4 Study Population and Entry Criteria

# 4.1 Number of Participants

Approximately 700 participants will be randomized (5:2) to atogepant 60 mg QD (500 participants) or oral SOC migraine prevention medication (200 participants) at approximately 115 centers in the United States. A minimum of 200 participants randomized to atogepant must be classified as *De Novo* Participants (see definition below).

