## 7.5 Sample Size Calculation

This study plans to randomize a total of 700 participants. Participants will be randomized 5:2 to receive atogepant 60 mg QD or oral SOC migraine prevention medication. Based on data from previous studies (Aurora 2011; Rapoport 2006), it is estimated that approximately 60% of those participants will complete 6 months of treatment, and of those, 65% will complete 12 months of treatment.

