11.1 Adverse Events

Adverse events will be coded by system organ class and preferred term using the Medical Dictionary for Regulatory Activities (MedDRA), version 21.0 or newer.

An AE will be considered as a treatment-emergent adverse event (TEAE) if the AE began or worsened (increased in severity or became serious) on or after the date of the first dose of open-label study treatment. For participants randomized to the atogepant arm, an AE that occurs more than 30 days after the last dose of open-label study treatment or Visit 16 whichever comes later will not be counted as a TEAE. For participants randomized to the SOC arm, an AE that occurs after Visit 16 will not be counted as a TEAE. Per case report form instructions, a new AE record will be created for any AE that worsens; therefore, for participants randomized to the atogepant arm, TEAEs can be identified as those AEs with recorded onset date on or after the date of the first dose of open-label study treatment within 30 days after the last dose of open-label study treatment or Visit 16 whichever comes later. For participants randomized to the SOC arm with available Visit 16 information, TEAEs can be identified as those AEs with recorded onset date on or after the date of the first dose of open-label study treatment and up to Visit 16; for participants randomized to the SOC arm but missing Visit 16 information, TEAEs are identified as those AEs with recorded onset date on or after the date of the first dose of open-label study treatment. An AE will be considered as a treatment-emergent SAE (TESAE) if it is a TEAE that also meets SAE criteria. TEAEs that started after the date of last dose of study treatment will be considered as newly emergent.

Overall summary of AEs will be provided on a per-participant basis for categories of TEAEs, treatment-related TEAEs, deaths, TESAEs, and TEAEs leading to study discontinuation.

The number and percentage of participants reporting TEAEs in each treatment group will be tabulated by system organ class and preferred term, and further categorized by severity to the study treatment.

The number and percentage of participants reporting treatment-related TEAEs in each treatment group will be tabulated by system organ class and preferred term.

The number and percentage of participants reporting newly emergent TEAEs in the atogepant arm will be tabulated by system organ class and preferred term.

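### The visible SAP 11.1 tables give each on-treatment adverse-event category as one crude percentage per arm, so they cannot show whether risk changes between the first and second half of the year

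*SAP*

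**What the plan says.** Protocol 2.1 sets the objective as the "safety and tolerability of treatment with atogepant 60 mg QD when administered over 52 weeks". Protocol 3.1 describes "a 52-week treatment period, and a safety follow-up period of 4 weeks". Protocol 7.5 expects that "approximately 60% of those participants will complete 6 months of treatment, and of those, 65% will complete 12 months of treatment".

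The main table in SAP 11.1 is specified as follows: "The number and percentage of participants reporting TEAEs in each treatment group will be tabulated by system organ class and preferred term", with a further split by severity. Treatment-related TEAEs, TEAEs leading to discontinuation, common TEAEs (at least 2% in any arm) and serious TEAEs (TESAEs) are likewise given per arm by system organ class and preferred term.

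The counting window is longer than the treatment period. In the atogepant arm the event excluded as too late is "an AE that occurs more than 30 days after the last dose of open-label study treatment or Visit 16 whichever comes later". In the SOC arm the window closes at Visit 16.

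One table depends on timing: "TEAEs that started after the date of last dose of study treatment will be considered as newly emergent". It is tabulated for the atogepant arm only.

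SAP 9.1 summarizes participant-years and counts participants reaching successive treatment durations, but only as exposure. The visible text uses neither as a denominator for adverse events.

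**The concern.** Protocol 1.2 describes an earlier Phase 2/3 study with a 12-week treatment period. Much of what a 52-week study adds is information on later months. A reader of the final report will want to know whether an event type appears early and settles, continues at a steady rate, or emerges late.

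A single crude percentage over everyone treated cannot answer that. Planned drop-out makes it harder, because an event that arises only in months 7-12 can occur only in those still under observation, while the denominator remains all who started. The late risk is diluted, and the pooled figure carries no sign of the dilution. One exposure-adjusted rate for the whole period would not help, since it also averages over time.

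**Working it through.** **Inputs.** From the documents: "This study plans to randomize a total of 700 participants" (Protocol 7.5), allocation 5:2 (Protocol 4.1), and retention of 60% at 6 months and 65% of those at 12 months (Protocol 7.5, repeated in SAP 15). My assumptions: drop-out is exponential within each half-year and unrelated to the event, and the event rates are illustrative.

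**1. The plan's own figures.** 700 × 5/7 = 500 and 700 × 2/7 = 200, which matches Protocol 4.1. Expected atogepant completers are 500 × 0.60 = 300 at 6 months and 300 × 0.65 = 195 at 12 months (39%). For SOC they are 120 and 78.

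**2. Exposure by half-year, atogepant.** The drop-out hazards are −ln(0.60)/0.5 = 1.022 and −ln(0.65)/0.5 = 0.862 per year.
- Months 1-6: 500 × (1 − 0.60)/1.022 = 196 participant-years.
- Months 7-12: 500 × 0.60 × (1 − 0.65)/0.862 = 122 participant-years.
- Late share: 122/318 = 38%. It is 37.5% if all drop-out falls at the end of each half-year, 38.2% if linear and 39.4% if all at the start, so the assumed shape matters little.

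**3. Two risk patterns with the same pooled figure.** Take 10 of 500 = 2%. A simple rate is events divided by participant-years. A first-event model with drop-out competing gives slightly higher values.

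| Pattern | Simple rate per 100 participant-years | First-event model |
|---|---|---|
| Constant over 12 months | 10/318 = 3.1 | 3.2 |
| Months 7-12 only | 10/122 = 8.2 | 8.4 |

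The late-only rate is about 2.6 times the constant one, yet both print as 2%. A single exposure-adjusted rate for the whole period would be 3.1 per 100 in both cases. At a pooled 5% the model rates are 8.1 and 21.6 per 100.

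**4. Dilution.** A true 6-month risk of 5% arising only in months 7-12 appears as 2.4% of 500. To reach the 2% threshold of the common-TEAE table, a late-only event needs a true 6-month risk of about 4.1%.

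**5. What a split by half-year shows for the pooled 2%.**

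| Pattern | Months 1-6 | Months 7-12 |
|---|---|---|
| Constant | 6.2 events in 196 participant-years = 3.2 per 100 | 3.8 in 122 = 3.1 per 100 |
| Late only | 0 in 196 = 0 | 10 in 122 = 8.2 per 100 |

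**6. How the table could mislead if built carelessly.**
- *Unequal intervals with crude percentages.* With cuts at Days 84, 168 and 252 and an open last interval, that interval lasts at least 112 days against 84 for the others. A constant 3.5% per year then prints as 0.73%, 0.73%, 0.73% and 0.95%, an apparent rise of about 30% (0.95/0.73 = 1.30) where there is none.
- *Mismatched denominators.* TEAEs still count for at least 30 days after the last atogepant dose. About 35, 27 and 19 atogepant participants stop in the 30 days before Days 84, 168 and 252. If the denominator is those still on treatment at the start of an interval, their later events enter a numerator whose denominator excludes them.

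**The case against.** The strongest case against is that this is an optional supplement to a descriptive study, and that other displays already show time. Laboratory values, vital signs and ECG parameters are summarized at each postbaseline timepoint (SAP 11.2 to 11.4). C-SSRS is presented separately for treatment and follow-up (SAP 11.5). ALT/AST elevations are adjudicated and listed. Deaths, SAEs and discontinuations have separate displays, and AE start dates are recorded (Protocol 6.4.1). All of this stands. A reader might infer that a conclusion of 52-week safety would rest on one pooled percentage; the documents do not support that. None of these displays, however, gives a TEAE rate by time with the participants still at risk as denominator.

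Three other strong readings also fail. First, a reader might infer that every TEAE table covers exactly 52 weeks and ignores timing. The window runs past week 52, and the newly emergent table isolates post-dose onset in the atogepant arm, although it does not separate month 2 from month 10. Second, a reader might infer that early follow-up dominates the pooled figure. A 62/38 split of participant-years is not domination. Third, a reader might infer that such a table is absent from the whole plan. Table specifications are in a separate document (SAP 4) and parts of the SAP are blacked out, so the point is limited to the visible text.

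The objection about precision also stands. Ten events in 122 participant-years is 8.2 per 100, with an exact Poisson 95% interval of about 3.9 to 15.1 (chi-square limits 4.80 and 18.39 events, each divided by 121.9).

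**Conclusion.** The point holds for TEAEs in the visible SAP 11.1 text. The planned percentages are valid summaries, but they cannot distinguish a constant risk from one that changes over the year. With the plan's retention, a pooled 2% is compatible with about 3.2 per 100 participant-years throughout or about 8.2 to 8.4 per 100 confined to months 7-12. The two patterns share the pooled percentage, not the late hazard: if the months 7-12 hazard were equal in both, the late-only pattern would print a lower figure.

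The arm sizes and retention are the sponsor's; the drop-out shape, its independence from the event, and the event rates are assumed. This is a worthwhile improvement to the analysis, not an error that invalidates a planned table.

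**What to change.** Add to SAP 11.1 one descriptive table by arm of first onset in Days 1-182 and from Day 183 to the end of treatment, for any TEAE, TESAEs, TEAEs leading to discontinuation and common TEAEs. In each interval give the number at risk at its start, the participant-years at risk, the number with a first event and the rate per 100 participant-years. Using a rate keeps unequal interval length and drop-out from creating a false trend.

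State the basis for at-risk time so that it matches the numerator. Either restrict to on-treatment onsets with on-treatment time and show post-last-dose onsets separately, or extend at-risk time through the TEAE window. For the SOC arm, where Protocol 3.1 lets participants go without a preventive and later restart, use time in study from first dose.

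The cost is a small set of table shells. Onset dates are already collected and participant-years already planned, so no new data or visits are needed. The downside is few events and wide intervals in the later period, so the table should be labelled descriptive.

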11.2 Clinical Laboratory Assessments

Descriptive statistics for clinical laboratory values (in both SI and conventional units) at baseline, postbaseline, and changes from baseline values at each postbaseline timepoint will be presented by treatment group for the following laboratory parameters:

Allergan SAP 3101-302-002 AGN-241689

Hematology: Hemoglobin, hematocrit, red blood cell count, red blood cell

indices (mean corpuscular volume, mean corpuscular hemoglobin, mean corpuscular hemoglobin concentration), white blood cell count, including differential (neutrophils, lymphocytes, monocytes, eosinophils, and basophils),

platelet count

Chemistry: Sodium, potassium, chloride, bicarbonate, glucose, blood

urea nitrogen, creatinine, total bilirubin, alkaline phosphatase, aspartate aminotransferase, alanine

aminotransferase, lactate dehydrogenase, creatine kinase, total protein, albumin, calcium, phosphorus, uric acid, total

cholesterol

Urinalysis: Specific gravity, pH

In addition, descriptive statistics for values and changes from the baseline values in conventional units at each assessment time point will be presented for selected clinical laboratory parameters listed in Appendix I. A description of reporting the lab values in conventional units in patient narratives (along with the standard reporting in SI units) is presented at the end of Appendix I.

Clinical laboratory test values will be considered potentially clinically significant (PCS) if they meet either the lower-limit or higher-limit PCS criteria listed in Table 11-1. The normal range for eGFR was not specified by the lab. Therefore, eGFR<60 mL/min/1.73m² is defined in Table 11-1 to classify renal function as the category of "Moderate eGFR Decrease or Worse" based on FDA guidance on PK studies in patients with impaired renal function. The number and percentage of participants who have PCS postbaseline clinical laboratory values will be tabulated by treatment group. The percentages will be calculated relative to the number of participants with available non-PCS baseline values and at least 1 postbaseline assessment. The numerator will be the total number of participants with available non-PCS baseline values and at least 1 PCS postbaseline value during the study. A supportive tabular display of participants with PCS postbaseline values will be provided, including the PID number, baseline and all postbaseline (including non-PCS) values.

[figure not shown]
In addition, a tabular display showing all AEs that occurred in participants who had PCS postbaseline clinical laboratory values will be provided.

Potential Hy's Law criteria within a 24-hour window is defined by a postbaseline elevation of alanine aminotransferase (ALT) or aspartate aminotransferase (AST) \geq 3 x ULN, along with total bilirubin (TBL) \geq 2 x ULN and a non-elevated alkaline phosphatase (ALP) \leq 2 x ULN, all based

on blood draws collected within a 24-hour period. Potential Hy's Law criteria without time window is defined by maximum of post baseline elevation of ALT or AST \geq 3 x ULN, along with maximum of post baseline elevation of TBL \geq 2 x ULN. Patients who meet the potential Hy's Law criteria from the first dose of study drug to the end of study will be summarized. Supportive tabular displays will also be provided.

[figure not shown]

The number and percentage of participants meeting each of the following criteria for postbaseline hepatic laboratory abnormalities listed in Table 11-2 will be summarized by treatment group. The percentages will be calculated relative to the number of participants with at least 1 available postbaseline assessment. The numerator will be the total number of participants having at least 1 postbaseline value that meets the specific category during the study. A supportive listing will also be provided.

Table 11-2 Criteria for Hepatic Laboratory Abnormalities Allergan

The number and percentage of participants with an adjudicated case (i.e., $ALT \ge 3 \times ULN$) and/or $AST \ge 3 \times ULN$) will be summarized by treatment group and by relationship of ALT or AST elevation to study medication. The percentages will be calculated relative to the number of participants with an adjudicated case. The numerator will be the number of participants with an adjudicated case in the specific category of relationship. If a participant has more than 1 adjudicated case, he or she will be counted in the most relevant category of relationship.

Participants with an adjudicated case (i.e. $ALT \ge 3 \times ULN$ or $AST \ge 3 \times ULN$) will be listed with their ALT and AST assessments, adjudication dates, relationship of ALT or AST elevation to study medication, and confounding factor(s). Additional listings will be provided for participants who meet $ALT \ge 3 \times ULN$ or $AST \ge 3 \times ULN$ and/or potential Hy's law and have one of the following categories: at least 1 abnormal liver biochemistry risk factor, at least 1 liver disease sign and symptom, at least 1 liver diagnostic test performed, consultation with a specialist for liver evaluation, liver lab tests performed, and drug screen performed, respectively.

[figure not shown]
A listing of urine pregnancy test results will be provided for female participants of child-bearing potential with at least one positive result.

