#### 5.4 Treatment Allocation Ratio

Participants will be randomized to the following 2 arms in a 5:2 ratio:

- Atogepant 60 mg QD (n = 500)
  - Note: A minimum of 200 participants randomized to atogepant must be classified as De Novo Participants
- Oral SOC migraine prevention medication (n = 200)

[figure not shown]
No stratification will be performed.

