11.4 Electrocardiograms

[figure not shown]
Descriptive statistics for ECG parameters (ie, heart rate, PR interval, QRS interval, RR interval, QT interval, and QTc interval) at baseline, postbaseline, and changes from baseline values at each postbaseline timepoint will be presented by treatment group.

ECG parameter values are considered PCS if ECG values meet either the actual value or change from baseline PCS high criteria listed in Table 11-4. The number and percentage of participants with PCS postbaseline values will be tabulated by treatment group. The percentages will be calculated relative to the number of participants with an available non-PCS baseline value and at least 1 postbaseline assessment. The numerator will be the total number of participants with an available non-PCS baseline value and at least 1 PCS postbaseline ECG value during the study. A supportive listing of participants with PCS postbaseline values will be provided. A listing of all AEs for participants with PCS ECG values will also be provided.

Table 11-4 Criteria for Potentially Clinically Significant Electrocardiograms

To evaluate ECG postbaseline values of clinical interest, the number and percentage of participants with post-treatment QTcF > 450 msec, > 480 msec, and > 500 msec will be tabulated by treatment group.

The number and percentage of participants with an increase > 30 msec but \le 60 msec, and with an increase > 60 msec in QTcF will be tabulated. Participants will be counted only once for the most severe category. A supportive listing of participants with postbaseline QTcF increases > 30 msec will be provided, including the PID number, study center, and all QTc values (including changes from baseline). A listing of all AEs for participants with postbaseline QTcF increases > 30 msec will also be provided.

A shift table from baseline to the end of open-label treatment period in the investigator's overall interpretation of the ECG will be presented by treatment group for the following categories: normal; abnormal, not clinically significant; abnormal, clinically significant. A tabular display of participants with postbaseline clinically significant ECG abnormalities according to the investigator's overall interpretation will be provided.

[figure not shown]

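### Does the ALT/AST adjudication table in SAP 11.2 need a by-arm percentage of participants assessed, besides the share of adjudicated cases?

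*SAP*

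**What the plan says.** SAP 11.2 plans several by-arm displays of liver laboratory findings.

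- **Adjudication table.** The number and percentage of participants with an adjudicated case (ALT and/or AST at least 3 x ULN) "will be summarized by treatment group and by relationship of ALT or AST elevation to study medication". The denominator is stated: "The percentages will be calculated relative to the number of participants with an adjudicated case". A participant with several cases enters once: "he or she will be counted in the most relevant category of relationship".
- **Hepatic laboratory abnormalities (Table 11-2).** Number and percentage by arm: "The percentages will be calculated relative to the number of participants with at least 1 available postbaseline assessment". The rows of this table are not visible in the public text.
- **Listing.** Participants with an adjudicated case "will be listed with their ALT and AST assessments, adjudication dates, relationship of ALT or AST elevation to study medication", together with confounding factors.

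Potentially clinically significant (PCS) laboratory values in the same section use participants at risk: "The percentages will be calculated relative to the number of participants with available non-PCS baseline values and at least 1 postbaseline assessment". PCS ECG values in SAP 11.4 do the same: "The percentages will be calculated relative to the number of participants with an available non-PCS baseline value and at least 1 postbaseline assessment".

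The SAP introduction (section 4) places the specifications of tables, figures and listings in a separate document. Protocol 3.3 gives relatedness of the elevation to atogepant as the purpose of adjudication.

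**The concern.** The adjudication table is laid out by treatment group, but its only percentage is conditional on being a case. A reader used to the neighbouring tables could take it for an incidence. Protocol 3.1 gives comparative safety data as the reason for the standard-of-care (SOC) arm, and Protocol 6.4.2 makes ALT or AST of at least 3 x ULN an event of special interest. For such an event one would like to see, by arm, the percentage of assessed participants with a case in each relationship category. No visible text plans that figure.

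Two further points add to the doubt. The SAP does not say whether the denominator is the cases in the arm or the cases in both arms. The arms are also unequal ("Participants will be randomized to the following 2 arms in a 5:2 ratio"), so a pooled denominator would give different percentages even at equal risk. If the table were misread, a difference in hepatic risk could be hidden or invented.

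**Working it through.** **Inputs.** 700 randomized 5:2, giving 500 atogepant and 200 SOC (Protocol 4.1 and 5.4). Denominators are from SAP 11.2. The documents give no event rate, so all case counts and rates below are assumptions. All randomized participants are taken as assessed.

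**1. Arm sizes.** 700 x 5/7 = 500 and 700 x 2/7 = 200, as stated.

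**2. What the within-arm share can and cannot show.** Share = related cases / adjudicated cases in the arm. Risk = related cases / participants assessed in the arm. Entries are atogepant v SOC.

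| Example | Adjudicated | Related | Share related | Related / assessed | Risk ratio |
|---|---|---|---|---|---|
| A | 10 v 4 | 5 v 2 | 50% v 50% | 1.0% v 1.0% | 1 |
| B | 20 v 2 | 10 v 1 | 50% v 50% | 2.0% v 0.5% | 4 |
| C | 4 v 4 | 2 v 2 | 50% v 50% | 0.4% v 1.0% | 0.4 |

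The share is the same in all three examples while the risk ratio runs from 0.4 to 4. The share is silent on incidence, as any attribution percentage is.

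**3. The pooled reading.** At equal risk p, atogepant would hold 500p / (500p + 200p) = 5/7 = 71.4% of all cases and SOC 2/7 = 28.6%, a ratio of 2.5 whatever p is. These are totals over all relationship categories. For the related category in example A, the pooled figures are 5/14 = 35.7% and 2/14 = 14.3%, again a ratio of 2.5. The distortion is real under this reading, but the reading is unlikely. The table is by treatment group, and the rules for Table 11-2, PCS laboratory values and PCS ECG values do not say within arm either. Nobody would compute those three over both arms.

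**4. Can the reader get the missing figure?** Three planned outputs are enough.

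- Numerator: the count by arm and relationship category, printed in the adjudication table and checkable against the listing.
- Denominator: participants with a value after baseline in the arm, already used for Table 11-2.
- Result: one division. In example B, 10/500 = 2.0% and 1/200 = 0.5%.

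**5. An arm without a case.** With 200 SOC participants, the probability of no case is (1 - p)^200: 0.367 at p = 0.5%, 0.134 at 1% and 0.018 at 2%. The share is then undefined, but the count of zero is printed and 0/200 can still be reported.

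**6. What an added percentage would be worth.** It would be crude. Protocol 7.5 expects 0.60 x 0.65 = 39% to complete 12 months, so it would need to be read with the participant-years by arm that SAP 9.1 already plans.

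**The case for a change.** The strongest argument for a change is consistency. The other by-arm safety displays quoted here count participants at risk, and SAP 11.1 gives treatment-related adverse events, on investigator causality, as a number and percentage of participants in each arm. The committee's judgement is the more standardized of the two in an open-label trial, yet it has no such percentage. Table 11-2 is a laboratory summary and is not described as split by adjudicated relationship, so it cannot fill that cell. The remedy would be one sentence and one column.

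This is right as far as it goes: the by-arm percentage in each relationship category is not planned in the visible text. It does not show a fault. The table is there to describe attribution, which is what adjudication is for, and a share of cases is a valid measure of attribution. It is also not true that only shares are given, because the counts stand beside them. The overall incidence cannot be called absent, since the SAP defines an adjudicated case by a laboratory threshold and Table 11-2, whose rows are not visible, may well hold that threshold. Column labels and secondary columns belong to the separate table specifications.

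One wording difference also stands. Protocol 3.3 speaks of relatedness to atogepant, SAP 11.2 of relatedness to study medication in both arms. Which was judged for the SOC arm depends on the adjudication charter, which is not available here. The two texts should be reconciled with the charter before the relationship split is compared between arms. That concerns interpretation and does not show the table to be wrong.

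**Conclusion.** No change to the plan follows. The adjudication table reports attribution among cases, correctly labelled by its stated denominator and accompanied by counts. The one figure not planned in the visible text, the by-arm percentage of assessed participants in each relationship category, follows by a single division from outputs already planned. Stating that the share is taken within arm and adding the crude percentage would be a convenience to the reader; it would add no information.

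The range of risk ratios from 0.4 to 4 at an identical share shows why the share must not be read as a risk. It is not an error in a planned result. It rests on assumed case counts with 500 and 200 assessed. The 2.5-fold distortion needs the pooled reading, which the layout by treatment group does not support. The conclusion assumes that the counts and the listing are produced as the SAP describes and that analysts take the denominator within arm.
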